8.2. Exploratory Efficacy Variable(s) and Analysis

8.2.1. Change in daily “ON” time without troublesome dyskinesia (“GOOD ON”) from Baseline to each visit

The changes from baseline to all post-baseline visits within each treatment regimen and the difference between the 2 treatment regimens in “GOOD ON” time (defined as the sum of "ON" time without dyskinesia and “ON” time with non-troublesome dyskinesia) will be estimated using a Mixed Model for Repeated Measures (MMRM). The model includes response data from all post-baseline visits with no imputation for missing data. The “GOOD ON” time at baseline will be included as a covariate and the treatment regimen (Regimen 1 or Regimen 3), visit (Month 1, 3, 6, 9 or 12) and the interaction between treatment regimen and visit will be included as fixed factors in the model. An unstructured covariance structure will be assumed and the denominator degrees of freedom will be computed using the Kenward-Roger method. In case the model will not converge

with the unstructured covariance structure, the heterogeneous compound symmetry (CSH) and the heterogeneous Toeplitz structure (TOEPH) will be used instead (in that order). Both the changes from baseline within each treatment regimen and the difference between the regimens will be estimated, separately for each visit, from the same MMRM using contrasts. Since ON/OFF diaries were assessed differently for Cohort 1, this cohort will be excluded from the model.

The changes in “GOOD ON” time will be estimated both as hours (normalized to 16 hours of awake time) and as a percentage out of awake time during the 24 hours of data collection. However, only one p-value will be provided due to the fact that the p-values will be identical.

The SAS code planned for the analysis is outlined below.

```
PROC MIXED DATA=DATA;  
CLASS TRTP AVISIT USUBJID;  
MODEL CHG=BASE TRTP AVISIT TRTP*AVISIT / SOLUTION DDFM=KR;  
REPEATED AVISIT / SUBJECT=USUBJID TYPE=UN;  
LSMEANS TRTP*AVISIT / PDIFF CL;  
WHERE AVISIT IN ('MONTH 1', 'MONTH 3', 'MONTH 6', 'MONTH 9', 'MONTH 12' ) AND COHORT=2;  
RUN;
```

8.2.2. Change in daily “OFF” time based on home "ON/OFF" diaries from Baseline to the 12-month visit

The daily “OFF” time will be analyzed similarly as the “GOOD ON” time replacing baseline “GOOD ON” time with baseline “OFF” time as covariate.

8.2.3. Change in daily “ON” time without any dyskinesia (troublesome or non-troublesome) based on home "ON/OFF" diaries from Baseline to the 12-month visit.

The daily “ON” time without any dyskinesia will be analyzed similarly as the “GOOD ON” time replacing baseline “GOOD ON” time with baseline “ON” time without any dyskinesia as covariate.

8.2.4. Proportion of responders at the 12-month visit based on daily “OFF” time recorded in home "ON/OFF" diaries. A responder is defined as a subject that experiences $\geq 50\%$ reduction in “OFF” time from Baseline.

The proportion of patients fulfilling the response criterion will be tabulated by visit. In addition, cumulative percentage of patients with reduction in “OFF” time normalized to a 16-hour waking day will be plotted as a function of percent reduction in “OFF” time from baseline to Month 12..

8.2.5. Change in daily “ON” time with troublesome dyskinesia in a subset of subjects who had more than 1 hour of troublesome dyskinesia at Baseline based on home “ON/OFF” diaries from Baseline to the 12-month visit.

The daily “ON” time with troublesome dyskinesia in the subset of subjects who had more than 1 hour of troublesome dyskinesia at Baseline will be analyzed similarly as the “GOOD ON” time replacing baseline “GOOD ON” time with baseline “ON” time with troublesome dyskinesia as covariate.

8.2.6. Change in PDQ-39 summary index and the 8 dimension scores from Baseline to the 12-month visit

The PDQ-39 summary index and the 8 dimension scores will be analyzed similarly as the “GOOD ON” time replacing baseline “GOOD ON” time with baseline PDQ-39 as covariate.

8.2.7. Change in EQ-5D-5L scores from Baseline to the 12-month visit

The health state dimensions will be evaluated by presenting the distribution of responses separately for each of the 5 dimensions at each visit. In addition, the categorical changes (improved, same, and worsened) will be summarized for each of the 5 dimensions at each visit. The VAS score and the health state index score will be analyzed similarly as the “GOOD ON” time replacing baseline “GOOD ON” time with baseline VAS or health state index score as covariate

8.2.8. Change in UPDRS Part II (ADL) from Baseline to the 12-month visit.

The UPDRS Part II (ADL) score change from baseline will be analyzed similarly as the “GOOD ON” time replacing baseline “GOOD ON” time with baseline UPDRS Part II as covariate.

8.2.9. Change in CGI-Severity (CGI-S) and CGI-Improvement (CGI-I) from Baseline to the 12-month visit

The distribution of categorized data (Improvement, non-improvement) will be summarized for each visit using frequencies and percentages. In addition, the distribution of the original uncategorized values will be summarized with frequencies and percentages.

8.2.10. Change in SGI-Improvement from Baseline to the 12-month visit.

The SGI-I will be analyzed similarly as the CGI-I.

8.2.11. Change in PDSS total score from Baseline to the 12-month visit.

The PDSS total score will be analyzed similarly as the “GOOD ON” time replacing baseline “GOOD ON” time with baseline PDSS as covariate.

8.2.12. Change in UPDRS Part III (motor score) from Baseline to the 12-month visit.

The UPDRS Part III (Motor) score will be analyzed similarly as “GOOD ON” time replacing baseline “GOOD ON” time with baseline UPDRS Part III score as covariate.

8.2.13. Morning Akinesia: Change from baseline to month-12 in percentage of “OFF” time during the first 3 hours since the subject is awake after 06:00 (6 am)

The change from baseline to month 12 in percentage of “OFF” time during the first 3 hours since the subject is awake after 06:00 (6 am) will be analyzed similar to the “GOOD ON” endpoint replacing baseline “GOOD ON” time with percentage of OFF during the first 3 hours since the subject is awake at baseline.

8.3. Subgroup analysis

Subgroup analyses will be performed for factors defined in section 4.5 of this document. Each subgroup will be analyzed separately for each regimen in “GOOD ON” time endpoint using MMRM model similar to the model specified in section 8.2.1 including additional fixed factors for the subgroup variable and 2 level interaction terms between the visit, and subgroup variable. The influence of each subgroup on the change from baseline will be investigated per visit using the p-values for the interaction terms. In addition, forest plot depicting the LS mean changes and 95% CI for each subgroup will be displayed.

```
PROC MIXED DATA=DATA;  
CLASS SUBGROUP AVISIT USUBJID;  
MODEL CHG=BASE SUBGROUP AVISIT SUBGROUP*AVISIT / SOLUTION DDFM=KR;  
REPEATED AVISIT / SUBJECT=USUBJID TYPE=UN;  
LSMEANS SUBGROUP*AVISIT / PDIFF CL;  
WHERE AVISIT IN ('MONTH 1', 'MONTH 3', 'MONTH 6', 'MONTH 9', 'MONTH 12' ) AND COHORT=2;  
BY TRTP;  
RUN;
```

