4.5. Sub-group Analysis Sets

The following subgroups may be explored, e.g. for the “ON” time without troublesome dyskinesia:

ND0612H-012

Final 4.0

- Patients with the baseline “ON” time without troublesome dyskinesia less than or equal to the median versus patients with baseline “ON” time without troublesome dyskinesia above the median
- Patients with low total daily levodopa dose at baseline (<400 mg) versus patients with high total daily levodopa dose at baseline (\geq 400 mg)
- Non-elderly (<65 years) versus elderly (\geq 65 years) patients
- Male versus female patients
- Patients with 1 hour or more of troublesome dyskinesia at baseline vs. Patients with less than 1 hour.
- Patients enrolled in USA versus EU+Israel (Eastern+Western+Israel)

In case any subgroup analysis will be performed, the corresponding demographic and baseline data will be summarized.

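### SAP 8.3 judges subgroup influence by the visit-by-subgroup interaction p-values, which flag a gap that is constant over visits only at the false-positive rate

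*SAP*

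**What the plan says.** SAP 4.5 lists six two-level factors: baseline GOOD ON time split at the median, baseline levodopa dose, age, sex, baseline troublesome dyskinesia and region. SAP 8.3 analyses each of them for GOOD ON time with an MMRM like that of 8.2.1, one regimen at a time and in Cohort 2 only.

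The text of 8.3 adds a main effect for the subgroup variable and "2 level interaction terms between the visit, and subgroup variable". It then names the measure: "The influence of each subgroup on the change from baseline will be investigated per visit using the p-values for the interaction terms". The code agrees with the text on the model: "MODEL CHG=BASE SUBGROUP AVISIT SUBGROUP*AVISIT / SOLUTION DDFM=KR", run by regimen over Months 1, 3, 6, 9 and 12. It contains no other interaction. It also requests "LSMEANS SUBGROUP*AVISIT / PDIFF CL", and the text promises a "forest plot depicting the LS mean changes and 95% CI for each subgroup will be displayed".

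SAP 8.2.1 uses the parallel line "LSMEANS TRTP*AVISIT / PDIFF CL" for the regimen comparison, but its text says that "the difference between the regimens will be estimated, separately for each visit, from the same MMRM using contrasts". Section 8.3 has no such sentence.

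SAP 5.3 sets a two-sided 0.05 level with nominal p-values and no multiplicity adjustment.

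**The concern.** The question in 8.3 is whether subgroup membership affects the change from baseline. The statistic it names answers a different one: whether the difference between the levels varies over time. The two coincide only when the gap changes across visits.

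A roughly constant gap from Month 1 to Month 12 is an ordinary pattern. For that pattern, a report that follows 8.3 literally could conclude that age, sex, dyskinesia or region has no influence although one level does better at every visit. Other printed output (the same-visit contrasts and the SUBGROUP main effect) could point the other way. The SAP would then name the uninformative statistic as the measure, and the choice between the two would be made after the results are seen.

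**Working it through.** The documents give no power, SD, effect size or error rate for the subgroup analysis, so there is no planned figure to reproduce. The inputs taken from the SAP are five visits, two levels per factor and two-sided alpha 0.05.

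**1. What the interaction p-values test.** Let g_v be the gap between levels at visit v. The interaction coefficients are g_v − g_ref, four of them for five visits. The overall SUBGROUP*AVISIT test is a 4-df test of g_M1 = g_M3 = g_M6 = g_M9 = g_M12. If g_v = g at every visit, all four coefficients equal g − g = 0 and the non-centrality is 0. The rejection rate is then alpha = 5% for any g and any sample size. This needs no assumption about SD or correlation.

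Nor can these p-values serve a per-visit reading: there is one overall p-value, or four coefficients for five visits.

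**2. Simulation check.** With BASE as covariate, SD 3 h, compound symmetry 0.5, 40 per level and 4,000 replicates:

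| Constant gap | Overall interaction | Any of 4 coefficients | SUBGROUP main effect | Month 12 contrast |
|---|---|---|---|---|
| 1.5 h | 5.0% | 15.4% | 81.2% | 59.7% |
| 3 h | 5.6% | 15.3% | 100% | 99.3% |

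With no gap at all, any-of-four is 16.0%. Over the other covariance patterns and reference visits tried, any-of-four runs from 12.6% to 17.2%; four independent tests would give 1 − 0.95^4 = 18.5%.

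**3. What the same-visit difference would detect.** Assumptions, not in the documents: SD of change 2.5-3.5 h, between-visit correlation 0.3-0.7, 20-75 patients per level, equal levels, complete data, constant 1.5 h gap. Formula: SE = SD × √(2/n), non-centrality = 1.5/SE, non-central t with 2n − 3 df.

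| n per level, SD | SE (h) | Non-centrality | Month 12 power | Two level CIs do not overlap |
|---|---|---|---|---|
| 20, 3.5 h | 1.107 | 1.36 | 26% | 8% |
| 40, 3.0 h (central) | 0.671 | 2.24 | 60% | 29% |
| 75, 2.5 h | 0.408 | 3.67 | 95% | 81% |

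- With 30% fewer patients at Month 12, the powers are 19%, 45% and 86%.
- In the central case, a 1.0 h gap gives 31% and a 2.0 h gap 84%. The interaction test stays at 5% for both.
- CI non-overlap requires |t| above √2 times the usual critical value, so reading the forest plot in that way is less sensitive than the contrast.

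**4. SUBGROUP main effect (printed, not named as the measure).** The SD of the five-visit mean is SD × √((1 + 4ρ)/5). In the central case this is 3 × √(3/5) = 2.32 h, non-centrality 2.89, power 81%. The range is 33% (n 20, SD 3.5, ρ 0.7) to over 99% (n 75, SD 2.5, ρ 0.3).

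**5. Where the interaction test does work.** For a gap rising evenly from 0.3 to 1.5 h, the squared deviations from the mean gap sum to 0.90. The non-centrality is (n/2) × 0.90/[SD² × (1 − ρ)], which in the central case is 20 × 0.90/4.5 = 4.0. Power is 30%, with a range of 10% (n 20, SD 3.5, ρ 0.3) to 94% (n 75, SD 2.5, ρ 0.7). The test is valid for changing gaps, but it is not a test of influence.

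**6. Baseline median split.** One factor splits GOOD ON time "without troublesome dyskinesia less than or equal to the median versus patients with baseline" value above it, while continuous BASE is also in the model. Assume a linear slope of −0.5, baseline SD 2.5 h and 80 patients. The simulated unadjusted difference between halves is −1.97 h and the BASE-adjusted difference is 0.04 h. A linear baseline effect is absorbed by construction.

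**The case against.** The strongest reply is that the sentence says per visit, and the only coded output with a p-value for each visit is the PDIFF set from the SUBGROUP*AVISIT LS means. On this reading the authors meant the same-visit differences and described them loosely, as the likeness to 8.2.1 suggests. That may well have been the intent. It does not rescue the text: the preceding sentence defines the interaction terms as visit by subgroup, and a same-visit LS-mean difference is not an interaction term. Section 8.2.1 names the contrasts explicitly and 8.3 does not.

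Second, the analysis is exploratory. SAP 4.5 says subgroups may be explored, p-values are nominal, and 8.3 sets no rule for declaring no influence. A reader would also have the contrasts, the main effect and the forest plot. This stands and limits the weight of the point.

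Third, the power figures rest on assumed inputs. The protocol plans about 210 treated patients, which allows at most 105 per level; the SAP says 120-170. The analysed set is smaller still: Cohort 2, one regimen, with valid diaries. Cohort 2 enrolment to Regimen 1 ended with Protocol amendment 2, so fewer than 20 per level is plausible there. At 10 per level (SD 3 h, 1.5 h gap) the Month 12 contrast has about 18% power, and a 10 versus 70 split gives about 31%. So the gain may be modest in one regimen. The 5% result for the interaction test is unaffected. The 13-17% figure does depend on the assumed covariance and the reference visit, and applies only if someone scans the coefficients.

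**Conclusion.** The concern holds. As worded, 8.3 names a statistic that cannot detect a constant subgroup gap beyond its 5% false-positive rate, or about 13-17% if the four coefficients are scanned. The 5% is an algebraic identity. The comparison figures (Month 12 contrast 26% to 95%, central 60%, for a 1.5 h gap) rest on the assumed SDs and group sizes above, with equal levels and complete data.

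The consequence is confined to exploratory subgroup statements on GOOD ON time. The model and code are sound and the right output is already produced. The sentence should be corrected, but nothing in the primary safety analysis or the regimen-level estimates depends on it.

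**What to change.** In SAP 8.3, replace the sentence naming the interaction p-values with, for example: *The influence of each subgroup on the change from baseline will be assessed by the between-level difference in LS means at the same visit (estimate, 95% CI, nominal p-value), Month 12 foremost; the SUBGROUP*AVISIT test will be used only to describe whether this difference changes over visits.*

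Keep the model, the code and the factors of 4.5. Of the C(10,2) = 45 pairwise differences that PDIFF prints for each factor and regimen, 5 are same-visit and are the ones to report. Giving Month 12 priority matches the SAP's Month 12 efficacy endpoints.

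For the baseline GOOD ON median split, add a table note that the LS means are adjusted for continuous baseline, so this row should not be read as showing whether baseline matters.

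The cost is one sentence and one note, with no new programming of contrasts. The downside is more nominal p-values on display: 6 factors × 2 regimens × 5 visits = 60. Putting Month 12 first places the weight on 6 × 2 = 12 of them.

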9. STATISTICAL SOFTWARE

All data listings, summaries, and statistical analyses will be generated using SAS[®] version 9.3 or higher

10. CHANGE FROM ANALYSIS PLANNED IN PROTOCOL

- The version of SAP (3.0) was based on Clinical Study Protocol ND0612H-012 Version 8.0 (global Amendment 7): issued on 12 March 2019. At the time when the SAP version 3.0 was finalized, the sponsor endorsed FDA recommendation of a change in the safety primary analyses which were not yet reflected in the protocol. This change was intended to be introduced in a later protocol amendment
- The version of SAP (4.0) was based on Clinical Study Protocol ND0612H-012 Version 9.0 (global Amendment 8): issued on 11 July 2019. There are no changes from this current SAP version (4.0) to the amended protocol (V9.0).
